#### 5.5.1.4 **Supportive care considerations for ipilimumab administration**

##### 5.5.1.4.1 **Treatment of infusion reactions associated with ipilimumab**

Since ipilimumab contains only human protein sequences, it is less likely that any allergic reaction will be seen in patients. However, it is possible that infusion of ipilimumab will induce a cytokine release syndrome that could be evidenced by fever, chills, rigors, rash, pruritus, hypotension, hypertension, bronchospasm, or other

symptoms. No prophylactic pre-medication will be given unless indicated by previous experience in an individual patient. Reactions should be treated based upon the following recommendations.

- For mild symptoms (e.g., localized cutaneous reactions such as mild pruritus, flushing, rash):
  - Decrease the rate of infusion until recovery from symptoms, remain at bedside and monitor patient.
  - Complete the ipilimumab infusion at the initial planned rate.
  - Diphenhydramine 50 mg IV may be administered at the discretion of the treating physician and patients may receive additional doses with close monitoring.
  - Premedication with diphenhydramine may be given at the discretion of the investigator for subsequent doses of ipilimumab.
- For moderate symptoms (any symptom not listed above [mild symptoms] or below [severe symptoms] such as generalized pruritus, flushing, rash, dyspnea, hypotension with systolic BP > 80 mmHg):
  - Interrupt ipilimumab.
  - Administer diphenhydramine 50 mg IV.
  - Monitor patient closely until resolution of symptoms.
  - Corticosteroids may abrogate any beneficial immunologic effect, but may be administered at the discretion of the treating physician.
  - Resume ipilimumab infusion after recovery of symptoms.
  - At the discretion of the treating physician, ipilimumab infusion may be resumed at one half the initial infusion rate, then increased incrementally to the initial infusion rate.
  - If symptoms develop after resumption of the infusion, the infusion should be discontinued and

- no additional ipilimumab should be administered that day.
- The next dose of ipilimumab will be administered at its next scheduled time and may be given with pre-medication (diphenhydramine and acetaminophen) and careful monitoring, following the same treatment guidelines outlined above.
- At the discretion of the treating physician additional oral or IV antihistamine may be administered prior to dosing with ipilimumab.
- For severe symptoms (e.g., any reaction such as bronchospasm, generalized urticaria, systolic blood pressure < 80 mm Hg, or angioedema):
  - Immediately discontinue infusion of ipilimumab, and disconnect infusion tubing from the subject.
  - Consider bronchodilators, epinephrine 1 mg IV or subcutaneously, and/or diphenhydramine 50 mg IV, with solumedrol 100 mg IV, as needed.
  - Patients should be monitored until the investigator is comfortable that the symptoms will not recur.
  - No further ipilimumab will be administered.
- In case of late-occurring hypersensitivity symptoms (e.g., appearance within one week after treatment of a localized or generalized pruritus), symptomatic treatment may be given (e.g., oral antihistamine, or corticosteroids).

#### 5.5.1.4.2

#### **Treatment of Ipilimumab-Related Isolated Drug Fever**

In the event of isolated drug fever, the investigator must use clinical judgment to determine if the fever is related to the ipilimumab or to an infectious etiology. If a patient experiences isolated drug fever, for the next dose, pre-treatment with acetaminophen or non-steroidal anti-inflammatory agent (investigator discretion) should be instituted and a repeated antipyretic dose at 6 and 12 hours after

ipilimumab infusion, should be administered. The infusion rate will remain unchanged for future doses. If a patient experiences recurrent isolated drug fever following premedication and post dosing with an appropriate antipyretic, the infusion rate for subsequent dosing should be decreased to 50% of the previous rate. If fever recurs following infusion rate change, the investigator should assess the patient's level of discomfort with the event and use clinical judgment to determine if the patient should receive further ipilimumab.

#### 5.5.1.5 **Suggested evaluation and treatment for Immune Related Adverse Events (irAEs) associated with ipilimumab**

**NOTE:** This information has been summarized from the Ipilimumab Investigator Brochure (IB). Please refer to the current version of the IB for more details on the Suggested Work-up and Treatment for irAEs and Management Algorithms. Although these are suggested guidelines that take into consideration potential variations that may be required based on a specific clinical situation, these guidelines are strongly recommended.

Management algorithms for the early detection and treatment of ipilimumab associated toxicities are provided in Appendices [Appendix XII-Appendix XVII](#).

Gastrointestinal (diarrhea) and skin (rash)-related toxicities are the most common irAEs reported in previous studies with ipilimumab. Suggested evaluation procedures for suspected irAEs of the GI tract, liver, skin, eye, pituitary, and adrenal gland are described in the current version of the IB. When symptomatic therapy is inadequate or inappropriate, an irAE should be treated with systemic corticosteroids followed by a gradual taper.

##### 5.5.1.5.1 **Gastrointestinal Tract**

Diarrhea (defined as either first watery stool, or increase in frequency 50% above baseline with urgency or nocturnal bowel movement, or bloody stool) should be further evaluated and infectious or alternate etiologies ruled out. Subjects should be advised to inform the investigator if any diarrhea occurs, even if it is mild. An algorithm for managing subjects with

diarrhea or suspected colitis is provided in [Appendix XIV](#) and the IB.

Corticosteroid therapy is strongly recommended for ipilimumab related  $\geq$  Grade 3 diarrhea/colitis and should be slowly tapered according to symptomatic response over at least 1 month. Subjects with ipilimumab related Grade 2 diarrhea/colitis may be initially treated conservatively, but should be immediately switched to corticosteroids if symptoms persist or worsen. For more severe symptoms in patients with grade 1 or 2, prednisone 60 mg or equivalent may be required to control initial symptoms, and the dose should be gradually tapered over at least a 1-month duration. Lower doses of prednisone may be considered for less severe cases of colitis. It is suggested that prednisone (for oral administration) or solumedrol (for IV administration) be the corticosteroids of choice in the treatment of colitis.

If the diarrhea is prolonged or severe or is associated with signs of systemic inflammation or acute phase reactants (e.g., increased CRP or platelet count; or bandemia), it is recommended that sigmoidoscopy (or colonoscopy, if appropriate) with colonic biopsy of 3 to 5 specimens for standard paraffin block be performed. It is strongly recommended that these patients be hospitalized for I.V. corticosteroids and inpatient work-up. All subjects with confirmed colitis should also have an ophthalmologic examination, and a slit-lamp exam should be considered, to rule out uveitis. Also consider testing for stool calprotectin and stool WBCs as outlined in [Appendix XIV](#). Negative stool testing for calprotectin or WBCs does not rule out autoimmune colitis.

Infrequently, subjects will appear refractory to corticosteroids or will flare following taper of corticosteroids. In these subjects, unless contraindicated (i.e., sepsis and other serious infections, or perforation), a single dose of infliximab at 5 mg/kg may provide benefit.

Rev. 11/13

Rev. 2/12

Rev. 11/13

#### 5.5.1.5.2 Hepatotoxicity

Liver function tests should always be performed and reviewed prior to administration of all ipilimumab doses. In addition, subjects presenting with right upper quadrant abdominal pain, unexplained nausea, or vomiting should have LFTs performed immediately and reviewed before administering the next dose of study drug. A Hepatotoxicity Management Algorithm is provided in [Appendix XV](#) and the current IB.

LFTs  $\geq$  Grade 2 (for subjects with normal baseline LFT) or LFT  $\geq$  2 times baseline values (for subjects with baseline LFT of Grade 1 or 2) should prompt treating physicians to: (1) increase frequency of monitoring LFTs to at least every 3 days until LFT have stabilized or improved; (2) investigate to rule out non-irAE etiologies; and (3) initiate an autoimmunity evaluation. Disease progression, other malignancies, concurrent medications, viral hepatitis, and toxic etiologies should be considered and addressed, as appropriate. Imaging of the liver, gall bladder, and bile ducts should be considered to rule out neoplastic or other non-irAE-related causes for the increased LFTs. An ANA, perinuclear anti-neutrophil cytoplasmic antibody (pANCA), and anti-smooth muscle antibody test should be performed if an autoimmune etiology is considered. Consultation with a hepatologist is appropriate for a suspected liver IRAE and a biopsy should be considered.

Rev. 2/13

For rising LFTs, ipilimumab dosing should be held according to the dose delay/permanent discontinuation guidelines.

Rev. 2/13

For AST/ALT  $>$  5x the ULN or total bilirubin  $>$  3x the ULN, the following should be done: (1) ipilimumab should not be administered; (2) LFTs should be repeated every 24 hours until stabilization or improvement; and (3) therapeutic intervention with high dose steroids should be strongly considered (e.g., methylprednisolone 1-2 mg/kg once or twice daily or equivalent). If symptoms or LFT elevations are controlled, the corticosteroid dose should be gradually tapered over a

period of at least 1 month. Flare in LFTs during this taper may be treated with an increase in the dose of steroid and a slower taper. The most current experience with immune-related hepatitis has allowed further development of this management algorithm (see flow chart in [Appendix XV](#) and current IB) to include recommendations for treatment.

Rev. 2/13, 11/13

For rising LFTs with AST/ALT > 5X ULN or total bilirubin >3X the ULN or suspected immune-mediated hepatitis:

Rev. 2/13

- a. Admit subject to hospital for evaluation and close monitoring.
- b. Stop any further ipilimumab dosing per protocol (Section [5.5.1.2.3](#) of protocol).

Rev. 2/13

- c. Start at least 2 mg/kg methylprednisolone sodium succinate per day, given IV as a single or divided dose.
- d. Check liver laboratory test values (LFTs, T-bilirubin) daily until stable or showing signs of improvement for at least 3 consecutive days.
- e. If no decrease in LFTs after 3 days or rebound hepatitis occurs despite treatment with corticosteroids, then add mycophenolate mofetil 1g BID per institutional guidelines for immunosuppression of liver transplants (supportive treatment as required, including prophylaxis for opportunistic infections per institutional guidelines).
- f. If no improvement after 5 to 7 days, consider adding 0.10 to 0.15 mg/kg/day of tacrolimus (trough level 5-20 ng/mL)
- g. If target trough level is achieved with tacrolimus but no improvement is observed after 5 to 7 days, consider other immunosuppressive therapy per institutional guidelines and in consultation with hepatology.
- h. Continue to check LFTs daily for at least 2 weeks to monitor sustained response to treatment.

Rev. 2/13

5.5.1.5.3 **Pancreas**

Symptoms of abdominal pain associated with elevations of amylase and lipase, suggestive of pancreatitis, may rarely be associated with anti-CTLA-4 monoclonal antibody administration. The differential diagnosis of acute abdominal pain should include pancreatitis. Appropriate workup should include serum amylase and lipase tests.

5.5.1.5.4 **Skin**

A dermatologist should evaluate persistent or severe rash or pruritus. A biopsy should be performed if appropriate and if possible, photos of the rash should also be obtained. Any non-protocol drugs that could contribute to a drug reaction should be stopped if possible pending evaluation. Patients with low-grade ipilimumab-mediated skin toxicity (Grade 1 or 2) may remain on therapy and could be treated with symptomatic therapy (e.g., antihistamines). Low-grade symptoms persisting for 1 to 2 weeks and relapsing should be treated with topical or moderate dose oral corticosteroid therapy (e.g., prednisone 1 mg/kg once daily or equivalent). High-grade (persistent Grade 3 despite moderate dose oral corticosteroid such as prednisone 1 mg/kg once daily or equivalent or any Grade 4) symptoms require high-dose IV corticosteroid therapy (e.g., methylprednisolone 2 mg/kg once or twice per day or equivalent) to control initial symptoms. A skin biopsy should be performed if appropriate. Once rash or pruritus is controlled, the initiation of corticosteroid taper should be based on clinical judgment; however, the corticosteroid dose should be gradually tapered over a period of at least 1 month.

Patients with any high-grade skin related toxicity (Grade 3 regardless of causality) have to skip ipilimumab and may only continue treatment with ipilimumab if the initial symptoms have improved to  $\leq$  Grade 1, while patients with grade 4 skin toxicities have to permanently discontinue ipilimumab.

5.5.1.5.5

**Endocrine**

Subjects with unexplained symptoms such as fatigue, myalgias, impotence, mental status changes, or constipation should be investigated for the presence of thyroid, pituitary, or adrenal endocrinopathies. An endocrinologist should be consulted if an endocrinopathy is suspected. If there are any signs of adrenal crisis such as severe dehydration, hypotension, or shock, intravenous corticosteroids with mineralocorticoid activity (e.g., methylprednisolone) should be initiated immediately. If the patient's symptoms are suggestive of an endocrinopathy but the patient is not in adrenal crisis, endocrine laboratory results should be evaluated before corticosteroid therapy is initiated.

Endocrine work up should include at least Thyroid stimulating hormone and free T4 levels to determine if thyroid abnormalities are present. TSH, prolactin, and a morning cortisol level will help to differentiate primary adrenal insufficiency from primary pituitary insufficiency. Radiographic imaging (e.g., MRI) with pituitary cuts should be performed. If the pituitary scan and/or endocrine laboratory tests are abnormal and suggestive of pituitary endocrinopathy, a short course of high dose corticosteroids (e.g., dexamethasone 4 mg every 6 hours or equivalent) should be strongly considered in an attempt to treat the presumed pituitary inflammation, but it is currently unknown if this will reverse the pituitary dysfunction. Abrupt discontinuation of corticosteroids should be avoided due to possible prolonged adrenal suppression. Once symptoms or laboratory abnormalities are controlled, and overall patient improvement is evident, the initiation of steroid taper should be based on clinical judgment; however the corticosteroid dose should be gradually tapered over a period of at least 1 month. Appropriate hormone replacement therapy should be instituted if an endocrinopathy is documented, and it is possible that subjects may require life-long hormone replacement.

Patients diagnosed with hypophysitis should be permanently discontinued from additional ipilimumab therapy.

Please see [Appendix XVI](#) and the current IB for the Endocrinopathy Management Algorithm.

#### 5.5.1.5.6 **Eye**

Ocular inflammation (episcleritis or uveitis), usually in association with colitis, was reported in a few subjects. These conditions responded to topical corticosteroid therapy. An ophthalmologist should evaluate visual complaints with examination of the conjunctiva, anterior and posterior chambers and retina; visual field testing and an electroretinogram should also be performed. Patients with ipilimumab related uveitis or episcleritis have been treated with topical corticosteroid eye drops. On this study, the last dose of ipilimumab will be at approximately week 60. Ophthalmologic examination is strongly recommended at 6 and 18 months after start of treatment, to be performed by an ophthalmologist. If melanoma recurrence occurs before these time points, the ophthalmological examination should still be done if clinically indicated.

#### 5.5.1.5.7 **Neuropathies**

Isolated cases of motor neuropathy of an autoimmune origin have been reported among patients treated with ipilimumab. Three cases have been diagnosed as Guillain-Barre syndrome (GBS), two of which were considered study related. In both cases, the GBS was atypical in nature and more clinically resembled polyneuritis. As of 30 June 2009, 27 cases of neuropathy SAEs have been reported.

Of these, 22 were assessed as unrelated to study therapy because alternative etiologies, including brain metastases, spinal cord compression, arterial thrombosis, or platinum-based chemotherapy were identified in almost every case. Please see [Appendix XVII](#) and the current IB for the Neuropathy Management Algorithm.

Rev. 9/14

5.5.2 **ARMS B AND E: Patients receiving Interferon Alfa - 2b**

Induction therapy by the IV route in the first 4 weeks shall be evaluated separately from Maintenance in weeks 5-52; a patient requiring dose modification(s) in the first month will therefore commence month 2 without prejudice, at full dosage. Doses missed during treatment due to toxicity, patient compliance, holiday, etc. should not be made up.

Overview

If a patient requires a dose modification (details are listed below), treatment must first be held. The first modification then requires a 33% reduction of dosage (to 13.3 MU/m^2) and the second modification requires a 66% reduction of dosage (to 6.6 MU/m^2). A patient who requires a third dose modification will be removed from treatment. Dose re-escalation will not be attempted following resolution of toxicity that required dose interruption or attenuation. Please see the table below.

	Full Treatment	Dose Mod 1	Dose Mod 2	Dose Mod 3
Arm B or E Induction (Weeks 1-4): High Dose IFN Alfa - 2b	20 MU/m 	13.3 MU/m 	6.6 MU/m 	Off
Arm B or E Maintenance (Weeks 5-52): High Dose IFN Alfa - 2b	10 MU/m 	6.6 MU/m 	3.3 MU/m 	Off

**PLEASE NOTE:** If a patient experiences any of the toxicities listed below, the patient must have a dose modification as follows: treatment must be held until the toxicity returns to institution's normal limits, patient's baseline, or normal limits per Common Toxicity Criteria or as listed in the table under Section [5.5.2.8](#), then reduced per above.

**EXCEPTIONS:** For Grade 3 proteinuria without Creatinine or BUN elevation, dose should be held until return to Grade 2 toxicity. For Grade 2 weight loss observed over a period of one month, dose should be held until weight gain or stabilization.

The following are the most common toxicities observed with interferon. Guidelines for HDI Dose Modification and Discontinuation are also provided. These toxicities and their management guidelines are based on experience from previous studies (E1684, E1690, E1694) and the following 2 publications that may also serve as additional resources on the toxicities associated with HDI and their management:

Rev. 2/12  
Rev. 8/12

---

**NOTE:** Dose modifications may be done for toxicities related to HDI therapy even if they don't fit these guidelines if it is determined by the treating physician that it is in the best interest of the patient for safety reasons taking into consideration the overall clinical status of the subject. A note has to be made of such a modification.

Rev. 2/12

5.5.2.1 **Constitutional Toxicity**

Fever, chill, myalgia/arthralgia, fatigue, headache: these constitutional toxicities of the interferons and other biologics are observed in the first weeks of treatment. Fatigue may worsen during the course of therapy and require a dose modification. In general, dose modifications are done for grade 3 or higher toxicities.

5.5.2.2 **Myelotoxicity**

Leukopenia, anemia and thrombocytopenia are observed with acute and chronic interferon therapy. Dose modifications are indicated for grade 4 granulocytopenia and grade 3 thrombocytopenia.

5.5.2.3 **Hepatotoxicity**

Fatal hepatotoxicity has been observed in patients receiving sustained intensive high dosages of interferon, and close attention to the occurrence of hepatocellular enzyme abnormalities is warranted. Grade 3 or greater elevations of bilirubin, AST, ALT or alkaline phosphatase require dosage modification. Please refer to table under Section [5.5.2.8](#).

Rev. 8/12

5.5.2.4 **Nephrotoxicity**

Acute kidney injury of Grade 1 (CTCAE v.4) is an indication for dose modification and elevations of Grade 2 require withdrawal of therapy.

Rev. 8/12

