Hepatotoxicity (SGPT [ALT] SGPT [AST])	1. > 5 times normal (Grade 3 or 4) 2. 33% 3. Grade 1	1. > 5 times normal (Grade 3 or 4) 2. 66% 3. Grade 1	1. > 5 times normal (Grade 3 or 4) 2. Discontinue
Nausea	1. Grade 3 or 4 or if persistent for more than 2 weeks at Grade 2 2. 33% 3. Grade 1	1. Grade 3 or 4 or if persistent for more than 2 weeks at Grade 2 2. 66% 3. Grade 1	1. Grade 3 or 4 or if persistent for more than 2 weeks at Grade 2 2. Discontinue
Ocular toxicity	None	None	Discontinue for any ocular toxicity

Rev. 2/13

Renal	1. Grade 1 2. 33% 3. normal	1. Grade 1 2. 66% 3. normal	1. Grade 1 2. Discontinue 3. Elevations of Grade 2 or higher at anytime require withdrawal of therapy
Vomiting	1. Grade 3 or 4 or if persistent for more than 2 weeks at Grade 2 2. 33% 3. Grade 1	1. Grade 3 or 4 or if persistent for more than 2 weeks at Grade 2 2. 66% 3. Grade 1	1. Grade 3 or 4 or if persistent for more than 2 weeks at Grade 2 2. Discontinue
Weight loss	1. Grade 2 if observed over a period of one month and is unintentional 2. 33% 3. Continue at the reduced dose if no other limiting adverse events	1. Grade 2 if observed over a period of one month and is unintentional 2. 66% 3. Continue at the reduced dose if no other limiting adverse events	1. Grade 2 is if observed over a period of one month and is unintentional 2. Discontinue.

Rev. 2/13

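### The interferon text and the Section 5.5.2.8 table give different restart rules for Grade 2 weight loss; the table's Renal and liver rows also need clarifying

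*Combined protocol and SAP*

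**What the plan says.** Section 5.5.2 (Arms B and E) sets the order of any change in interferon dose: "If a patient requires a dose modification (details are listed below), treatment must first be held". The notice below its dose-step table adds that "treatment must be held until the toxicity returns to institution's normal limits, patient's baseline", or normal limits under the toxicity criteria, or the level listed in the Section 5.5.2.8 table. The dose is then reduced. An exceptions paragraph follows with two entries:

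- Weight: "For Grade 2 weight loss observed over a period of one month, dose should be held until weight gain or stabilization".
- Proteinuria: "For Grade 3 proteinuria without Creatinine or BUN elevation, dose should be held until return to Grade 2 toxicity".

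Section 5.5.2.7 confirms that Grade 2 weight loss over a month calls for a dose modification.

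Each row of the Section 5.5.2.8 table gives a trigger, a percentage reduction and a threshold for resumption. Three rows matter here:

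- Weight loss: same grade and period, limited to unintentional loss. The resumption entry is "Continue at the reduced dose if no other limiting adverse events".
- Renal: reduce at Grade 1, resume at normal. It then adds "Elevations of Grade 2 or higher at anytime require withdrawal of therapy".
- Liver: the row label begins "Hepatotoxicity (SGPT [ALT] SGPT [AST", with a trigger above five times normal and resumption at Grade 1.

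Section 5.5.2.3 states the liver trigger more widely, "Grade 3 or greater elevations of bilirubin, AST, ALT or alkaline phosphatase require dosage modification", and refers the reader to the table.

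**The concern.** A site may work from the prose or from the table, and for weight loss the two lead to different actions on the same finding. HDI is the comparator for both ipilimumab doses in the primary comparisons, and Section 5.5.2 says missed doses are not made up, so a longer hold is dose lost. What is at stake is consistent and safe dosing in Arms B and E, and a clear reading of HDI dose modifications and discontinuations when they are reported.

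The Renal and liver rows raise a milder version of the same problem. A reader of the table alone cannot tell whether isolated proteinuria falls under the Renal row, and finds no entry for two of the four liver tests that the text names.

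**Working it through.** The plan states no figure to reproduce on this point. The check sets text against table.

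| Finding | Text | Table (5.5.2.8) | Result |
|---|---|---|---|
| Grade 2 weight loss over one month | 5.5.2: hold until weight recovers or levels off | Unintentional loss only; carry on at the lower dose if nothing else is limiting | Conflict |
| Grade 3 proteinuria, creatinine and BUN not raised | 5.5.2: hold, return at Grade 2 | Renal row, scope not stated | Depends on scope |
| Grade 3 or higher bilirubin or alkaline phosphatase | 5.5.2.3: modify, see table | No row | Gap in table |

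**Weight loss.** Take a patient with unintentional Grade 2 loss over a month, no other limiting event, dose held as Section 5.5.2 requires, and weight still falling. Under the exceptions paragraph the dose stays held. Under the table row the patient may restart at the 33% reduction. If the loss was intentional, the text still triggers a hold and the table does not.

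Precedence does not settle it. The general rule in 5.5.2 accepts the table's resumption levels. The exceptions paragraph departs from that rule, yet the table keeps its own weight-loss row with another answer. The table heading points back to 5.5.2.1 to 5.5.2.7, but the exceptions paragraph comes before 5.5.2.1, so a reader who follows the pointer does not reach it.

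**Renal row.** There are two readings.

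- Narrow: Section 5.5.2.4 gives the same Grade 1 and Grade 2 rule for acute kidney injury. If the row is its tabular form, the proteinuria exception stands beside it without conflict.
- Broad: Section 8.2.11 lists proteinuria among interferon's renal effects. If the row covers it, the table withdraws therapy at Grade 2 or higher, while the text holds at Grade 3 and lets the patient return at Grade 2.

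**Liver row.** The text names four tests; the table covers two, both labelled SGPT. For Grade 3 bilirubin, a site using the default in 5.5.2 would wait for normal limits or baseline. A site borrowing the transaminase row would resume at Grade 1.

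**Size of a hold (illustration).** Section 5.2.2.3 plans three maintenance injections a week for 48 weeks: 3 × 48 = 144. A hold of h weeks misses 3h injections, a share of 3h/144. The documents give no hold length, so h is an assumption:

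- h = 1: 3/144 = 2.1%
- h = 4: 12/144 = 8.3%
- h = 8: 24/144 = 16.7%

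This is the cost of a hold, not the difference between the two rules. Because 5.5.2 requires a hold before any modification, the table route may also lose some doses.

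**The case against.** The best defence on weight loss is that the table entry sits under the threshold for resumption and can be read as what happens after the required hold. That removes any claim that the table involves no hold. It does not supply the missing condition: the text ties the restart to weight and the table does not.

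On proteinuria, a reader might infer that the same patient is certainly withdrawn under one rule and resumed under the other. The documents do not support that. The Renal row repeats the grades of 5.5.2.4 and, like it, speaks of elevations, and the exception applies only where creatinine and BUN are not raised. A side-effect list grouped by organ, as in 8.2.11, sets no dosing rule. What remains is a label whose scope is not stated.

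On the liver, a reader might infer that Grade 3 bilirubin goes unmanaged. It does not: the trigger stays in force in 5.5.2.3, the hold, reduction steps and default resumption level are in 5.5.2, and the table heading refers back to 5.5.2.3. What remains is the risk that a site using the table misses the trigger or applies a different resumption level.

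A note in 5.5.2 lets physicians modify outside the guidelines for safety if they record it. That permits departures but does not say which written rule is the default.

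Timing also counts. Adult accrual closed in August 2014, adolescent accrual was to remain open only until 2016, HDI lasts 52 weeks, and Section 9 refers to events in September 2018. On those dates planned HDI treatment would be over, so a correction now would mainly serve interpretation of the dosing data and any reuse of the table.

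**Conclusion.** The weight-loss rules conflict as written and should be reconciled. The Renal row is a scope ambiguity that becomes a conflict only if it covers proteinuria. The missing bilirubin and alkaline phosphatase entries, and the AST label, are gaps in the table rather than a missing rule in the protocol.

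The effect is on consistency and safety of dosing in Arms B and E. Alpha, power and the endpoint definitions are untouched. Nor is HDI the control throughout: Section 9.8.1 allows a low-dose versus high-dose ipilimumab comparison without it.

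Without HDI event rates, neither the number of patients affected nor the change in delivered dose can be stated. The 2.1% to 16.7% of maintenance injections rests on the assumed hold of 1 to 8 weeks.

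**What to change.** Align Section 5.5.2 (including its exceptions paragraph), 5.5.2.3 and 5.5.2.4 with the 5.5.2.8 table:

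1. State one weight-loss rule in both places: the trigger (including whether intentional loss counts), whether a hold comes first, and the condition for restarting.
2. Say whether the Renal row covers acute kidney injury or creatinine only, or also proteinuria. If it covers proteinuria, reconcile it with the exception.
3. Add bilirubin and alkaline phosphatase entries consistent with 5.5.2.3, or an explicit pointer to the default rule in 5.5.2.
4. Correct the AST label.

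The sponsor and investigators decide which rule stands; this point takes no view. The cost is a few lines in one table and the matching text. If no further amendment is planned, the report of HDI dose modifications should note that the two versions coexisted.
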